**Table 6: Criteria for Abnormal ECG Parameters by Age**

ECG parameter (unit)	Age (years old)	Abnormally Low	Abnormally High
HR (bpm)	6 to <8	< 65	> 115
	8 to <12	< 55	> 110
	12 to <16	< 50	> 105
	≥16	< 50	> 100
PR interval (msec)	6 to <8	--	> 160
	8 to <12	--	> 175
	12 to <16	--	> 180
	≥16	--	> 200
QRS interval (msec)	6 to <8	--	> 100
	8 to <12	--	> 105
	12 to <16	--	> 110
	≥16	--	> 120

## 9.10. PHYSICAL EXAMINATIONS

Physical examinations are performed obtained at screening and week 12. Physical examinations will not be summarized. Physical examinations will be listed.

## 9.11. NEUROLOGICAL EXAMINATIONS

Neurological examinations will be performed at screening and week 12. Each assessment (i.e. Mental Status, Cranial Nerves, Motor System, Gait and Balance, Tendon Reflexes, Sensation and Other) will include category of normal/abnormal and not clinical significant (NCS)/abnormal and clinical significant (CS).Neurological examinations will be listed.

## 9.12. ADHD SYMPTOMS

Based on input from the TEV-50717 Tourettes Syndrome Scientific Advisory Board (SAB), which contains experts in the area of child psychiatric and andin the attempt to identify possible symptoms consistent with ADHD symptomatology, the items below from C&A-GTS-QOL were chosen:

Summary statistics will be provided to the observed values and change from baseline. This analyses are only exploratory and for signal detection purpose.

## 9.13. CHILDREN'S DEPRESSION INVENTORY, SECOND EDITION (CDI-2)

The CDI-2 (parent and self-report versions) is administered at screening, baseline, and weeks 2, 4, 6, 9, 12, and 13. As the CDI-2 is designed for children 7 to 17 years of age, children 6 years of age at baseline will not complete the Self-report version; the caregiver/adult will complete the Parent version.

The CDI-2 self-report is a 28-item self-report questionnaire assessing depressive symptoms in children 7 to 17 years of age with basic reading and comprehension skills. In the CDI-2, children are asked to choose 1 of 3 statements that most closely aligns with their feelings in the previous 2 weeks. The CDI-2 Self-report version contains 6 subscales (emotional problem, negative mood/physical symptoms, negative self-esteem, functional problems, ineffectiveness, interpersonal problems). The raw score is the sum of all subscales scores, ranging from 0 to 56, with higher score

indicating more severe depressive symptoms. The raw score is normalized to T-score (range: 40-90) based on patient's age and gender.

The CDI-2 parent is a 17-item questionnaire administered to parents to assess depression-related behaviors observed in their children. In the CDI-2 Parent, parents are asked to rate their child's behaviors in the past 2 weeks on a 4-point Likert scale from "not at all" to "much or most of the time". The CDI-2 parent version contains 2 subscales (emotional problems and functional problem). The raw score is the sum of the 2 subscales, ranging from 0 to 51, with higher score indicating more depression-related behaviors observed in their children.

The CDI-2 parent version and self-report versions subscale scores, raw scores, and self-report version T scores will be presented at baseline and each visit each is measured.

#### **9.14. COLUMBIA-SUICIDE SEVERITY RATING SCALE (C-SSRS)**

The C-SSRS children's baseline/screening scale assesses past and current suicidal ideation and behaviors to determine suicide risk and is administered at screening. The C-SSRS children's since last visit (SLV) scale is administered at baseline and at weeks 2, 4, 6, 9, 12, and 13. Patients will be placed into categories for suicidal ideation and for suicidal behavior based on their responses to various questions.

The suicidal ideation categories will be determined as follows by examining the response to the 5 questions under Suicidal Ideation.

Type	Section
Suicidal ideation	
(0) None – if response is No to Questions 1 and 2
 
(1) Wish to be Dead – if response to Question 1 is Yes and responses to Questions 2-5 are No.
 
(2) Non-Specific Active Suicidal Thoughts – if response to Question 2 is Yes and response to Questions 3-5 are No.
 
(3) Active Suicidal Ideation with Any Methods (Not Plan) without Intent to Act – if response to question 3 is Yes and response to questions 4 and 5 are No.
 
(4) Active Suicidal Ideation with Some Intent to Act, without Specific Plan – if response to Question 4 is Yes and response to Question 5 is No.
 
(5) Active Suicidal Ideation with Specific Plan and Intent – if response to Question 5 is Yes.

For suicidal behavior, the following categories will be used. The categories will be determined based on the response to the questions under suicidal behavior.

Type	Section
Suicidal behavior	
(6) Preparatory Acts or Behavior – if response to Preparatory Acts and Behavior is Yes and responses to Actual Attempt, Interrupted Attempt, Aborted Attempt, and Completed Suicide are No
 
(7) Aborted Attempt – if response to Aborted Attempt is Yes and responses to Actual Attempt, Aborted Attempt, and Completed Suicide are No.
 
(8) Interrupted Attempt – if response to Interrupted Attempt is Yes and response to Aborted Attempt, and Completed Suicide are No.
 
(9) Actual Attempt – if response to Actual Attempt is Yes and Completed Suicide is No.
 
(10) Completed Suicide - if response to Completed Suicide is Yes
 
(0) None – if responses to all the above 4 questions are No.

Suicidal ideation or behavior will be derived as the highest suicidal ideation or behavior score at the visit. Score of 0 represent “No Suicidal Ideation/Behavior”.

The frequency and percentage of suicidal ideation, suicidal behavior, suicidal ideation or behavior, and self-injurious behavior without suicidal intent will be summarized by treatment and overall, and visit. For baseline/screening version at baseline, past 2 years scores will be summarized.

Frequency and severity of suicidal ideation or behavior will also be summarized, using a shift table to examine changes in above C-SSRS scores from baseline compared to the worst (highest) category during the treatment period, by treatment and overall.

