4.2. Patient Exclusion Criteria

Patients will not be enrolled in this study if they meet any of the following criteria:

- a. Patient has a neurologic disorder other than TS that could obscure the evaluation of tics.

- b. The patient's predominant movement disorder is stereotypy (coordinated movements that repeat continually and identically) associated with autism spectrum disorder.
- c. Patient has a confirmed diagnosis of bipolar disorder, schizophrenia, or another psychotic disorder.
- d. Patient has clinically significant depression at screening or baseline.

Note: Patients receiving antidepressant therapy may be enrolled if on a stable dose for at least 6 weeks before screening.

- e. Patient has a history of suicidal intent or related behaviors within 2 years of screening:
 - previous intent to act on suicidal ideation with a specific plan, irrespective of level of ambivalence, at the time of suicidal thought
 - previous suicidal preparatory acts or behavior
- f. Patient has a history of a previous actual, interrupted, or aborted suicide attempt.
- g. Patient has a first-degree relative who has completed suicide.
- h. Patient has clinically significant OCD at baseline that, in the opinion of the investigator, is the primary cause of impairment.
- i. Patient has received CBIT for TS or CBT for OCD within 4 weeks of screening.
- j. Patient has received any of the following concomitant medications for tics within the specified exclusionary windows of first dose:
 - within 3 months: Depot neuroleptics, botulinum toxin, or tetrabenazine
 - within 4 weeks: cannabidiol oil and valbenazine
 - within 21 days: Reserpine
 - within 14 days: Neuroleptics (oral), typical and atypical antipsychotics (see [Appendix A](#)), metoclopramide, levodopa, and dopamine agonists

Note: Use of stimulant medications, including amphetamine, methylphenidate, and lisdexamfetamine, is allowed if primary use is for the treatment of ADHD and dosing has been stable for at least 2 weeks before screening and no changes to dose or frequency are anticipated during the course of the study.

Note: Use of atomoxetine is allowed if the primary use is for the treatment of ADHD and dosing has been stable for at least 4 weeks before screening and no changes to dose or frequency are anticipated during the course of the study.

Note: Use of benzodiazepines is allowed if primary use is not for tics, and dosing has been stable for at least 4 weeks before screening.

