If a relevant change in status is identified, patients will be seen immediately for an unscheduled visit by the study investigator and discussed with the medical monitor. The patient will be referred for further psychiatric evaluation if there is any suspected suicidal ideation with any level of intent, suicidal behavior, or clinical findings suggesting that the patient may be dangerous to self or others, and/or experiencing depression. The investigator will record these symptoms as an adverse event of depression and/or suicidality. If it is determined by the investigator, after consultation with the medical monitor and the consulting psychiatrist, that exposure to the IMP may have contributed to the adverse event of depression or suicidality, IMP will be immediately discontinued and the patient will be terminated from the study. Follow up

with a pediatric psychiatrist or licensed child and adolescent mental health clinician will be arranged.

In cases where it is determined that IMP did not contribute to the adverse event of depression or suicidality, the investigator will consult with the medical monitor and/or sponsor to determine whether the patient should continue in the study.

A reference sample is provided in [Appendix E](#).

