### **9.4. ADVERSE EVENTS**

Adverse events will be collected and recorded from the time a patient signs the informed consent to the end of follow-up period. For this study, the follow-up period for recording of adverse events is defined as 1 week of washout for patients who will participate in the open-label safety extension study TV50717-CNS-30047 and 2 weeks after the last dose of IMP for patients who will not roll over into Study TV50717-CNS-30047.

For all AEs, preferred AE terms and system organ class (SOC) will be coded using terminology from the Medical Dictionary for Regulatory Activities (MedDRA), version 20.1 or higher.

A treatment emergent adverse event (TEAE) is defined as an AE that begins after the first administration of study medication or existing AEs that worsen after the first dose of study medication. All reported AEs will be listed, but only TEAEs will be summarized in tables.

Drug related AEs will be considered those to be reasonable possibility based on the investigators assessment. Missing relationship will be considered as “Related”.

Unless otherwise specified, AEs will be summarized by SOC and PT, with SOCs and PTs within SOCs presented in descending order of patient incidence.

AE summary tables are listed below:

- An overall summary of the number and percentage of patients reporting any TEAEs, serious TEAEs, treatment-related TEAEs, serious treatment-related TEAE, any TEAEs leading to study drug discontinuation, any TEAEs leading to patient study drug interruption, and TEAEs leading to death. The overall summary will also be prepared by age group (6-11 years, or 12-16 years);
- TEAEs overall and by SOC and PT;
- TEAEs by severity, overall and by SOC and PT. Missing severity, if any, will be assumed as “severe”;
- Serious TEAEs, overall and by SOC and PT;
- Serious treatment related TEAEs, overall and by SOC and PT
- TEAEs by relationship to study treatment, overall and by SOC and PT;
- TEAEs leading to study drug discontinuation, overall and by SOC and PT;
- TEAEs leading to study drug interruption, overall and by SOC and PT;
- TEAEs leading to dose reduction overall and by SOC and PT;
- Most common TEAEs, overall and by PT. Most common TEAEs are defined as TEAEs that occur in > 4% of the patients in either of the treatment groups;
- SMQs for suicide/self-injury, depression (exclude suicide and self-injury), and Parkinson-like events.

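### SAP 9.14 defines the aborted-attempt category so that no patient can meet it, leaving an aborted attempt (without an actual attempt or completed suicide) with no suicidal-behavior category

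*SAP*

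**What the plan says.** The C-SSRS is a listed safety endpoint (Protocol 2.3.4 and 9.7.1; SAP 4.5 and 9). SAP 9.14 turns the five behavior items into one category in rising order: 6 preparatory acts, 7 aborted attempt, 8 interrupted attempt, 9 actual attempt, 10 completed suicide, and 0 for none.

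- Rule (6) requires all four more severe items to be No.
- Rule (7) applies "if response to Aborted Attempt is Yes and responses to Actual Attempt, Aborted Attempt, and Completed Suicide are No".
- Rule (8) applies "if response to Interrupted Attempt is Yes and response to Aborted Attempt, and Completed Suicide are No".
- Rule (9) needs an actual attempt without a completed suicide, and rule (10) a completed suicide.
- Rule (0) applies "if responses to all the above 4 questions are No", although five behavior items stand above it.

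The category feeds three outputs. The first is the by-visit frequency table. The second is a combined score: "Suicidal ideation or behavior will be derived as the highest suicidal ideation or behavior score at the visit". The third is a summary "using a shift table to examine changes in above C-SSRS scores from baseline compared to the worst (highest) category during the treatment period".

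**The concern.** Rule (7) names Aborted Attempt on both sides of its condition. Rule (8) names Aborted Attempt as an exclusion where the SAP's ordering calls for Actual Attempt. Read as printed, an aborted attempt can never appear as an aborted attempt in the derived data.

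This is a rare but serious outcome in a pediatric trial of a CNS-active drug, and one lost case changes what a table shows. The SAP also does not say what the combined score becomes when the behavior category is absent. If the absent category is simply ignored and the patient endorses no ideation, the score is 0, which Section 9.14 defines as no suicidal ideation or behavior.

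**Working it through.** The plan states no figure to reproduce. The check is to apply the printed rules to every possible set of answers.

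**Inputs.** Rules (6) to (10) and (0) are taken from SAP 9.14. Write P, Ab, In, Ac and Co for Preparatory, Aborted, Interrupted, Actual and Completed. Rule (0) is taken to mean that all five items are No.

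| Rule | Condition as printed | Condition implied by the SAP's ordering |
|---|---|---|
| 6 | P=Yes; Ab, In, Ac, Co=No | same |
| 7 | Ab=Yes; Ac, **Ab**, Co=No | Ab=Yes; **In**, Ac, Co=No |
| 8 | In=Yes; **Ab**, Co=No | In=Yes; **Ac**, Co=No |
| 9 | Ac=Yes; Co=No | same |
| 10 | Co=Yes | same |

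**Enumeration.** Five Yes/No items give 2^5 = 32 patterns. Rule (7) is met by 0 of them. The patterns that do not receive exactly one category are:

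| Items answered Yes | Rules met as printed | Category under the ordering |
|---|---|---|
| Ab | none | 7 |
| P, Ab | none | 7 |
| Ab, In | none | 8 |
| P, Ab, In | none | 8 |
| In, Ac | 8 and 9 | 9 |
| P, In, Ac | 8 and 9 | 9 |

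There are 2^3 = 8 patterns with Ab=Yes and Ac=No. Four have Co=Yes and score 10. The other four are the unassigned patterns above.

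**Sensitivity to rule (0).** Its count of four questions could mean that one item is left out. Under four of the five possible choices, all 4 patterns stay unassigned. If Aborted Attempt is the item left out, an isolated aborted attempt is classed as none, which is a false negative, and the other 3 stay unassigned.

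**Combined score.** Crossing the 4 unassigned patterns with the 6 ideation categories (0 to 5) gives 4 × 6 = 24 combinations.

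- *If an absent category is ignored:* all 24 score 0 to 5 instead of 7 or 8. The gap runs from 7 − 5 = 2 to 8 − 0 = 8 category codes. The codes are ordinal, so this gives rank only. In 4 of the 24 the score is 0.
- *If an absent category makes the score missing:* all 24 are missing.

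**Scale.** The documents give no expected number of such patients. As an illustration, assume all 58 patients planned for an arm are assessed and one has such an event. The arm should show 1/58 = 1.7% (exact 95% CI 0.04% to 9.2%) but would show 0/58 = 0% (upper limit 1 − 0.025^(1/58) = 6.2%).

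**Check of the correction.** Correcting rule (7) alone reduces the unassigned patterns from 4 to 2, because rule (8) still rejects Ab=Yes. Correcting (7) and (8), with (0) read as all five items No, puts each of the 32 patterns in exactly one category.

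**The case against.** The best defense is that this is a drafting slip with an obvious intent. The category title, the numbering and rule (6) all show what was meant. A condition that always returns zero records is likely to be noticed, and SAP Section 15 requires programs to be checked for their logic. The programming section (14) and the appendices (19) are almost wholly redacted, so the derivation actually programmed cannot be seen. All of this is fair, and it limits the finding to the printed rule. But no readable passage gives another derivation, and literal programming by two people would reproduce the same gap.

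The reach is also limited. The patient stays in the ideation table and in the listings (SAP 6.1). Under Protocol 7.9, "The investigator will record these symptoms as an adverse event of depression and/or suicidality". SAP 9.4 plans "SMQs for suicide/self-injury, depression (exclude suicide and self-injury), and Parkinson-like events". Clinical handling does not use these rules. Exclusion criterion f, "Patient has a history of a previous actual, interrupted, or aborted suicide attempt", makes this essentially a post-baseline matter. These points stand.

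SAP 6.3 says that missing values in safety analyses are generally not imputed. That bears on treating an absent category as 0 but does not settle how a maximum handles an absent component. The pattern counts are unweighted logical possibilities, and Section 9.14 plans only descriptive tables. They show that the fault exists, not how often it would occur.

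**Conclusion.** Wrong as written, and it should be corrected. Rule (7) cannot be met, and a patient with an aborted attempt, no actual attempt and no completed suicide receives no behavior category: 4 of 32 patterns, with rule (0) read as all five items No.

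The double assignment of 2 further patterns to categories 8 and 9 is minor. The highest-score rule settles it for the combined score and the shift table, leaving only the by-visit behavior table open. The miscount in rule (0) is a wording point, apart from the one reading that turns an isolated aborted attempt into none.

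The damage is confined to the derived behavior category and the outputs built on it, and it arises only if the text is programmed literally. Efficacy is untouched.

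**What to change.** Amend SAP 9.14 to follow its own ordering:

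- Rule (7): Aborted Attempt is Yes, and Interrupted Attempt, Actual Attempt and Completed Suicide are all No.
- Rule (8): Interrupted Attempt is Yes, and Actual Attempt and Completed Suicide are both No.
- Rule (0): all five behavior items are No.

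Rules (7) and (8) must be changed together. It would also help, though it is optional, to add one sentence on how a missing behavior category enters the combined score. After the correction this concerns only unanswered items.

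The cost is three lines of SAP text, one optional sentence and a check of one derivation in the analysis dataset. No new data are needed.

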## **10. PHARMACOKINETIC ANALYSIS**

Samples collected for PK analysis will be quantified for  $\alpha$ -HTBZ and  $\beta$ -HTBZ of TEV-50717, and other metabolites (as required), may be analyzed using population PK techniques. Analysis methods will be detailed in a separate exploratory population PK analysis plan.

## **11. INTERIM ANALYSES**

No interim analysis is planned.

## 12. CHANGE FROM ANALYSIS PLANNED IN PROTOCOL

A new exploratory endpoint is added:

■ [REDACTED]

## 14. PROGRAMMING CONSIDERATIONS

A horizontal bar chart showing the distribution of 1000 samples across 10 categories. The categories are represented by black bars of varying lengths. The first category has the longest bar, followed by category 9, category 8, category 7, category 6, category 5, category 4, category 3, category 2, and category 1 has the shortest bar. The bars are plotted against a white background with black outlines.

The figure consists of a 10x10 grid of black bars on a white background. The bars are of various lengths and are positioned in a staggered, non-overlapping manner. Some bars are aligned horizontally, while others are aligned vertically or at a 45-degree angle. The lengths of the bars vary significantly, creating a complex geometric pattern.

The image consists of a grid of horizontal bars of varying lengths. A central vertical column of bars is present, with the top bar being the longest. The bars are rendered in black on a white background.

The figure consists of a 7x2 grid of bar charts. The columns are labeled 'a' and 'b'. The rows are labeled 1 through 7. Each bar chart has a black bar on the left and a white bar on the right. The black bar represents the distribution of a variable for a specific category. The white bar represents the distribution of the same variable for a different category. The length of the bars indicates the magnitude of the variable. In column 'a', the black bars are generally longer than the white bars, except for row 1 where the white bar is longer. In column 'b', the white bars are generally longer than the black bars, except for row 1 where the black bar is longer. The distributions appear to be right-skewed, with a long tail extending to the right.

Topic	Percentage
Healthcare	98
Technology	95
Finance	92
Politics	90
Entertainment	88
Science	85
Food	82
Sports	78
Business	75
Art	72
History	68
Geography	65
Mathematics	62
Chemistry	58
Physics	55
Biology	52
Physics	50
Chemistry	48
Biology	45
Mathematics	42
Geography	40
History	38
Art	35
Business	32
Sports	30
Food	28
Science	25
Entertainment	22
Technology	20
Politics	18
Finance	15
Healthcare	12
Other	10

## **15. QUALITY CONTROL**

SAS programs are developed to produce output such as analysis data sets, summary tables, data listings, figures or statistical analyses. INC Research SOP 03.010 and 03.013 provide an overview of the development of such SAS programs.

INC Research SOP 03.009 describes the quality control procedures that are performed for all SAS programs and output. Quality control is defined here as the operational techniques and activities undertaken to verify that the SAS programs produce the output by checking for their logic, efficiency and commenting and by review of the produced output.

## 16. INDEX OF TABLES

## 17. INDEX OF FIGURES

Graph Number	Title	Population
1	Graph 1 Title	Population 1
2	Graph 2 Title	Population 2
3	Graph 3 Title	Population 3
4	Graph 4 Title	Population 4
5	Graph 5 Title	Population 5
6	Graph 6 Title	Population 6

**18. INDEX OF LISTINGS**

Listing Number	Title	Population

Listing Number	Title	Population

**19. APPENDICES**

A series of nine horizontal black bars of varying lengths and positions, suggesting a redacted list or sequence of items. The bars are arranged vertically, with some having irregular, stepped ends. The lengths of the bars range from approximately 10% to 90% of the page width.

Category	Approximate Sample Count
1	100
2	85
3	80
4	25
5	65
6	70
7	60
8	55
9	50
10	95

A horizontal bar chart consisting of 15 black bars of varying lengths. The bars are arranged in a descending order of length from left to right. The first bar is the longest, followed by a shorter bar, then a longer bar, and so on, ending with the shortest bar on the far right. The bars are set against a white background.

A horizontal bar chart consisting of 15 black bars of varying lengths. The bars are arranged in a descending order of length from left to right. The first bar is the longest, and the last bar is the shortest. The bars are set against a white background.
